8.5.3. Safety Monitoring for Platelet Count Results

All patients will have PLT counts monitored at least every 14 days (± 2 days) for the duration of the study Treatment Period, and at all post-treatment follow-up visits, and must not receive Study Drug without an interpretable PLT count result in the prior 14 days. Upon completion of the study Treatment Period, PLTs will be monitored at least every 14 days (± 2 days) for the first 6 weeks and then at 8 and 13 weeks Post-End of Treatment Period (as per visit schedule).

All PLT count results must be reviewed promptly (within 48 hours of receipt) by the Investigator or the designee to ensure that the count has not met a dose interruption or stopping rule. Actions to be taken in the event of reduced PLT count are shown in Table 2.

Platelet Count on Rx	Drug Dose	Monitoring
Normal range, ≥ 140 K/mm ³	No action	Monitor every 14 days (± 2 days)
Below values to be confirmed ideally within 3 days but no later than 7 days	If PLT count is confirmed, follow dosing guidance below:	If PLT count is confirmed, follow monitoring guidance below:
\geq 100K to < 140K/mm ³	No action	Monitor every 2 weeks
\geq 75K to < 100K/mm ³	Discussion with Medical Monitor***	Closer observation; monitor every week**
≥ 50K to < 75K/mm ³	Pause dosing. When ≥ 2 successive PLT count values return to ≥ 100 K/mm ³ restart dosing only if approved by Medical Monitor***	Closer observation
		Monitor every 2-3 days until 2 successive values show improvement
		Consider discontinuation of anticoagulants/ antiplatelet agents/non-steroidal anti-inflammatory drug (NSAIDs)
\geq 25K to < 50K/mm ³	Permanently discontinue Study Drug	Closer observation:
		Monitor daily until 2 successive values show improvement then monitor every 2-3 days until platelet count stable
		Discontinue anticoagulants/antiplatelet agents/, NSAIDs, while PLT count < 50K/mm ³ if possible
< 25K/mm ³	Permanently discontinue Study Drug	Closer observation:
		Monitor daily until 2 successive values show improvement then monitor every 2-3 days until platelet count stable Steroids and/or IVIG recommended****
		Consider referral to hematologist Discontinue anticoagulants/antiplatelet agents/NSAIDs medication while PLT count < 50K/mm ³ if possible

* Once a patient commences every 2-week monitoring this frequency of monitoring should continue until the platelet count returns to ≥ 140 K/mm³) for 2 successive values

** Once a patient commences weekly monitoring this frequency of monitoring should continue until the platelet count returns to ≥ 100 K/mm³) for 2 successive values.

*** The suitability of the patient for reduced, interrupted and/or continued dosing will be determined by the Investigator in consultation with the Medical Monitor and will be based on factors such as the original rate of decline in the patient's PLT count, whether any bleeding events were experienced by the patient, and the speed of recovery of PLT count after interruption of dosing.

**** Recovery in platelet count may be accelerated by administration of high-dose glucocorticoids. Treatment as recommended by the American Society of Hematology (ASH) (Neunert et al. 2019) guidelines for immune thrombocytopenia (Blood Advances, 10 DECEMBER 2019, Volume 3, Number 23) includes initial therapy with either dexamethasone 40 mg per day for 4 days, or prednisone 0.5 to 2.0 mg/kg per day. Prednisolone or prednisone may be administered for up to 2 to 4 weeks with taper; alternatively, intravenous immunoglobulin (IVIG) may be administered at 0.4 g/kg/d for 5 days, or infusions of 1 g/kg/d for 1-2 days (Provan et al. 2010; 2019).

Any case of a PLT count reduction to levels below $50,000/\text{mm}^3$ accompanied by a MB event or CRNMB event, or PLT count of $< 25,000/\text{mm}^3$ independent of a MB or CRNMB event, is considered an AESI and should be reported following the same requirements as for SAE reporting.

Table 3:Additional Lab Analyses for Patients with Platelet Count Less Than
50,000/mm³

The following is a list of lab analyses for patients who have any occurrence of platelet count less than 50,000/mm³. Archived samples prior to Day 1 of investigational treatment may also be analyzed in order to determine the patient's baseline conditions.

To Be Performed at Local Lab		
Peripheral smear (should be performed locally, fixed and sent to central lab for review)		
Fibrinogen split products or D-dimer on fresh blood		
To Be Performed at Central Lab		
Citrated sample for platelets		
Coagulation panel (PT/INR, aPTT)		
CBC with reticulocytes and mean platelet volume		
Total globulins: IgG and IgM		
Complement: total C3, total C4, C5a		
Serology for:		
HBV, HCV, HIV (if not done recently for screening)		
To Be Performed at Specialty Lab(s)		
Antiplatelet antibodies		
Anti-ASO antibody		

Note: These labs may be performed in the event of a platelet count less than 75,000/mm³ after discussion with the Study Medical Monitor. Additional lab tests may be considered in order to ascertain potential causative conditions for significant platelet count decreases / thrombocytopenia.

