6.2. Additional Study Assessments

6.2.1. Laboratory Assessments

Laboratory analyte samples will be collected throughout the study as per the Schedule of Procedures in Appendix A. A list of these analytes is contained in Appendix B.

Routine blood chemistry and lipid samples should be taken after fasting for at least 10 hours and preferably not more than 12 hours. Any confirmatory test, or test taken for safety reasons, may be taken at any time, irrespective of fasting status, but no later than 7 days after the initial result is obtained. During preparation for fasting samples, the patient can drink water and they should ensure that they consume sufficient water in order to not become dehydrated.

If tests are uninterpretable (e.g., due to clumping, hemolysis or quantity not sufficient) or missing, a repeat blood or urine specimen should be re-drawn as soon as possible (ideally within 1 week).

While on treatment, hematology samples will be collected at least every 14 days (± 2 days). In the event that a hematology sample is unreportable (e.g., due to hemolyzed or clumped blood samples), patient dosing cannot continue until another sample (central or local) is repeated and determined not to have met a platelet stopping rule.

Investigators may, at their discretion, test specific laboratory parameters which may be prone to clotting, clumping or hemolysis (e.g., hematology samples) at their local laboratory, in addition to the required central laboratory samples. In these instances, the local laboratory results should be recorded by the site into the electronic database. Assays which are blinded should not be locally tested and recorded into the database (e.g., lipid panel).

If there is no reportable platelet count within 14 days of the last platelet count, the Investigator will contact the patient to hold dosing until a new platelet count is obtained and reviewed.

While on treatment, blood and urine samples for renal function testing will also be collected every 14 days (± 2 days) and sent to the central laboratory for analysis for the first 3 months of the study treatment, and monthly thereafter during the Treatment Period per Section 8.5.2.

While on treatment, liver function testing will also be collected every 14 days (± 2 days) and sent to the central laboratory for analysis for the first 3 months of the study treatment, and monthly thereafter during the Treatment Period per Section 8.5.1.

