All lab samples are to be sent to the central laboratory by overnight courier and processed. Lab alerts issued will indicate the applicable protocol section to facilitate review and will be immediately and simultaneously sent by email to the Investigator, the Sponsor and the CRO Medical Monitors, the Sponsor Drug Safety Physician, and the Clinical Trial Manager (CTM), and should be received by them within 2 days from sample collection. All lab sample results from the site's local laboratories are received by the Study Center staff per the local laboratories' standard reporting time, and should be entered as soon as possible (ideally within 1 week) into the electronic Case Report Form (eCRF) to inform the Sponsor and CRO study monitoring teams.

All platelet count results must be reviewed promptly (within 48 hours of receipt) by the Investigator, or designee, to ensure that the count has not met a dose interruption or stopping rule. Any case of platelet count reduction to levels below $50,000/\text{mm}^3$ accompanied by a major bleeding (MB) event or clinically relevant non-major bleeding (CRNMB) event, or platelet count of $< 25,000/\text{mm}^3$ independent of a MB or CRNMB event, is considered an AE of special interest (AESI) and must be reported in an expedited fashion to the Sponsor as per Section 9.3.4 and Section 9.4.1.

All liver and renal function tests must also be reviewed promptly (within 48 hours of receipt) by the Investigator, or designee, to ensure that the result has not met the stopping rule.

All lab alerts received, including those related to platelet, liver, or renal function monitoring/stopping rules, are also reviewed promptly by the Sponsor and the CRO Medical Monitors who will agree on actions to be taken. Within 24 hours of receiving an actionable lab alert the CRO Medical Monitor will communicate instructions to the Investigator and the study personnel by emailing them the Safety Surveillance Form that needs to be completed and signed by the Investigator/study personnel and promptly returned to the Sponsor and CRO Medical Monitor. In urgent cases, such as platelets results below 50,000/mm³, or liver or renal test results reaching a critical stopping rule, the Investigator must also be contacted by phone.

Further information on safety monitoring and actions to be taken by the Study Investigator in the event of reduced platelet count are provided in Section 8.5.3 and Section 8.6.3.

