8.5. Safety Monitoring Rules

Stopping rules are described below in Section 8.6.

Please refer also to the 'Guidance for Investigator' section of the Investigator's Brochure.

- For the purposes of safety monitoring Baseline is defined as the average of the Day 1 pre-dose assessment and the last measurement prior to Day 1.
- In addition to the standard monitoring of clinical safety parameters, the following guidelines are provided for the monitoring of selected parameters chosen based on preclinical and clinical observations.
- In case of discrepancy between the test results from 2 sources, such as between the central and local lab, safety-mandated action must be initiated based on the more critical (lower or higher, as relevant) of the 2 values.

Confirmation Guidance: At any time during the study (Treatment or Post-Treatment Periods), the clinical laboratory results meeting any of the safety monitoring criteria presented below **must be confirmed** by performing measurements (ideally in the same laboratory that performed the

initial measurement) on new specimens. All new specimen collections should take place as soon as possible (ideally within 3 days but no later than 7 days of the initial collection). For stopping rules, if the initial laboratory result is observed during the Treatment Period, the results from the retest **must be available** prior to administering the next dose of Study Drug.

Re-dosing Guidance: In the event the initial laboratory result meets a stopping criterion, the results from the retest **must be available and reviewed by a Medical Monitor** prior to administration of the next dose of Study Drug (ISIS 678354 or placebo). In general, patients who do not meet the stopping rules based upon retest may continue dosing. However, the Investigator and the Sponsor Medical Monitor (or appropriately qualified designee) should confer as to at which dose Study Drug should be restarted, and whether additional close monitoring of the patient is appropriate. If any of the stopping criteria described below (refer to Section 8.6.1 through Section 8.6.3) are met, the patient will be permanently discontinued from further treatment with Study Drug (ISIS 678354 or placebo), evaluated fully as outlined below and in consultation with the Sponsor Medical Monitor or appropriately qualified designee, and will be followed up in accordance with Section 8.8 of the protocol.

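### After a first platelet count below 50,000/mm³, daily counts and the stop instruction for anticoagulants wait for a confirmatory sample whose only firm limit is 7 days, although that first result is already treated as urgent

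*Combined protocol and SAP*

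**What the plan says.** **Table 2 (protocol 8.5.3).** All bands below 140,000/mm³ share one confirmation window: "Below values to be confirmed ideally within 3 days but no later than 7 days". The monitoring column carries the condition "If PLT count is confirmed, follow monitoring guidance below", and no band is exempt. In both bands below 50,000/mm³ that column says "Monitor daily until 2 successive values show improvement then monitor every 2-3 days until platelet count stable", and it directs that anticoagulants, antiplatelet agents and NSAIDs be stopped where possible.

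**Confirmation window.** Section 8.5 asks for the new specimen at the earliest opportunity, "ideally within 3 days but no later than 7 days of the initial collection". Section 6.2.1, in a general sentence about confirmatory and safety samples and fasting, sets the limit differently: "but no later than 7 days after the initial result is obtained".

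**Action on the first result.** Under 6.2.1, laboratory alerts "should be received by them within 2 days from sample collection". "Within 24 hours of receiving an actionable lab alert the CRO Medical Monitor will communicate instructions to the Investigator". A platelet result below 50,000/mm³ is named as an urgent case in which the Investigator must also be phoned. The Table 3 laboratory work-up applies to any occurrence below 50,000/mm³, confirmed or not, and gives no deadline. Appendix A, footnote J, asks for expedited reporting of such a count.

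**Dosing.** The re-dosing paragraph of 8.5 begins "In the event the initial laboratory result meets a stopping criterion, the results from the retest" and goes on to require that they be available and reviewed by a Medical Monitor before the next dose.

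**The concern.** A first value of 139,000/mm³ and a first value of 24,000/mm³ have the same outer limit for the retest, yet Table 2 regards the second as serious enough for daily counts. Until confirmation, the protocol fixes no count schedule in the bands where it considers one necessary. What happens in that interval depends on what the Medical Monitor instructs in the individual case.

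This matters most for patients on oral anticoagulants, who are admitted by inclusion criterion 10d. Table 2 is the only text that directs these medicines to be stopped for a low platelet count, and that direction also waits for the retest. Elsewhere the protocol does act provisionally on a first value: section 8.5.2 interrupts Study Drug on a first renal alert and confirms afterwards.

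**Working it through.** The plan states no figure for this gap, so the stated time limits are added up.

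**Inputs.** Day 0 is the initial collection. The first result is from the central laboratory and known on Day 2 (6.2.1). The retest is drawn ideally by Day 3 and at the latest on Day 7 (8.5). A central retest is assumed to take the same 2 days; a local retest is assumed to be read the same day (6.2.1 permits local hematology).

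**Counting rule.** Daily counts start the day after the triggering result is known. Triggered by the first result, they would start on Day 3. As written, they start the day after the retest result. The days between are counts not required, leaving out the day of the retest, which is itself a count.

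Delay in the stop instruction = day the retest result is known − 2.

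| Retest | Result known | Days with no required count | Counts not required | Delay (days) |
|---|---|---|---|---|
| Local, Day 2 | Day 2 | none | 0 | 2 − 2 = 0 |
| Local, Day 3 | Day 3 | none | 0 | 3 − 2 = 1 |
| Central, Day 2 | Day 4 | 3, 4 | 2 | 4 − 2 = 2 |
| Central, Day 3 | Day 5 | 4, 5 | 2 | 5 − 2 = 3 |
| Local, Day 7 | Day 7 | 3, 4, 5, 6 | 4 | 7 − 2 = 5 |
| Central, Day 7 | Day 9 | 3, 4, 5, 6, 8, 9 | 6 | 9 − 2 = 7 |

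**Checks.**
- If daily counts start on the day a result is known, the last row still gives 6 (Days 2 to 6 and Day 8).
- Routine hematology every 14 ± 2 days does not fill the gap: the earliest routine count is Day 14 − 2 = 12, after Day 9.
- The Table 3 blood count or citrated sample could supply one count, but it is undated.

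**How likely is the event?** Section 2.3.4 reports no confirmed count below 100,000/mm³ in Phase 2. Section 2.3.3 reports one marked fall, in a monkey, at a human-equivalent dose of 840 mg per week. Against 80 mg every 4 weeks that is 840 × 4 / 80 = 42 times the higher study dose.

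**The case against.** The strongest defence is that the interval is already managed. Section 8.5 asks for a repeat without delay. Both Medical Monitors review alerts promptly and agree on action, the Investigator is phoned, and written instructions follow within 24 hours. Table 3 prompts a fresh draw, bleeding is treated at once under 8.5.4, and no further dose is given until the retest is reviewed. Confirming before escalating is also reasonable when platelet clumping can produce falsely low values. The renal rule in 8.5.2 has the same 7-day limit and requires no intensified testing before confirmation, so it is a precedent for provisional action but not for interim counts.

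All of this stands, and it lowers the severity. It does not close the gap: the prompt-repeat wording is a request, Table 3 is undated, and the content of the Medical Monitor's instruction is not specified.

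Four stronger readings are tempting, and the documents do not support them:
- **That nothing asks for a prompt repeat.** Section 8.5 does. What is missing is a firm limit under 7 days.
- **That a retest as late as Day 9 is allowed**, counting 7 days from a Day 2 result under 6.2.1. A site bound by both 6.2.1 and 8.5 must meet the earlier limit, which is Day 7.
- **That Table 2 contradicts 6.2.1.** The two can be read in sequence: alert, confirm, then count daily.
- **That 8.10.1 locks these medicines in place.** Its general rule against dose changes covers oral anticoagulants but does not name antiplatelet agents or NSAIDs. Section 8.5.7 encourages changes to statins, which the same rule covers as lipid-altering drugs, so safety sections are evidently meant to take precedence.

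**Conclusion.** The point holds as a mismatch of trigger and timing. Below 50,000/mm³ the protocol reacts urgently to the first result, but makes daily counts and the stop instruction conditional on a confirmation whose only firm limit is 7 days from collection. The size runs from nil to at most 6 daily counts not required and a 7-day delay in the written stop instruction.

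The upper end assumes a central first result on Day 2, a retest drawn on the last permitted day, a 2-day central turnaround, and no earlier count ordered by the Medical Monitor. A patient already on counts every 2 to 3 days in the band from 50,000 to below 75,000/mm³ would be largely covered. The gap mainly concerns an abrupt fall in someone on the 14-day schedule.

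It would be wrong to infer that dosing continues in the meantime, or that the patient is unprotected. With the expected rarity, this is a worthwhile low-cost improvement to a safety rule.

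**What to change.** Add to the Table 2 header, for any initial count below 50,000/mm³:
- draw a repeat count within 24 hours of the result, with a local laboratory allowed;
- continue counts daily until the value is confirmed or refuted;
- have the Investigator and Medical Monitor review anticoagulants, antiplatelet agents and NSAIDs at the first result.

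Keep confirmation as the condition for permanent discontinuation and for the steroid or IVIG recommendation, so that neither follows a spurious value. No new dosing hold is needed, because 8.5 already supplies one.

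The cost is a few lines of wording and a letter to sites. Local hematology is already permitted in 6.2.1, and SAP 4.2.4 already uses local platelet counts, so the analysis does not change. After a spurious first value, the repeat on Day 3 serves as the confirmation already required. Read locally the same day, it adds 0 draws; read centrally and known on Day 5, it adds 2 (Days 4 and 5).

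Two optional tidy-ups: state the same confirmation clock in 6.2.1, 8.5 and Table 2, and add an exception for Table 2 to the sentence on oral anticoagulant doses in 8.10.1.

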8.5.4. Safety Monitoring for Bleeding Events

Patients will be evaluated for occurrence of bleeding events continuously after the start of Study Drug treatment (Day 1) up to the end of the Follow-up Period. All bleeding events are considered AEs and reported on the AE case report form.

If an event a MB or CRNMB event occurs (as defined below), the Investigator must notify the Medical Monitor (or designee) and the patient should be treated, as needed, immediately and closely monitored (vital signs, lab tests such as hemoglobin (Hb), hematocrit (HCT), and PLT count, additional visits, overnight stays and coagulation tests may be needed if deemed appropriate by the treating physician) throughout the Treatment and Post-Treatment Evaluation Periods and an (S)AE case report form will be completed. In addition, approximately 2 mL of

K2EDTA anticoagulated blood will be collected and resulting plasma must be stored allowing for a centralized assessment of ISIS 678354 concentrations.

If a minor bleeding event occurs, the Investigator should notify the Medical Monitor (or designee) and additional testing of coagulation parameters (aPTT, PT, INR), PLT count, and PLT volume may be performed.

Major bleeding is defined as 1 of the following (Schulman and Kearon 2005):

- 1. Fatal bleeding
- 2. Symptomatic bleeding in a critical area or organ, such as intracranial, intraspinal, intraocular, retroperitoneal, intraarticular if in a major joint, or pericardial, or intramuscular with compartment syndrome
- 3. Clinically overt bleeding leading to transfusion of ≥ 2 units of packed RBCs or whole blood or a fall in Hb of 2.0 g/dL (1.24 mmol/L) or more within 24 hours

Clinically relevant non-major bleeding is defined as overt bleeding not meeting the criteria for MB but that resulted, for example, in medical examination, intervention, or had clinical consequences for a patient (Schulman and Kearon 2005).

- 1. Multiple-source bleeding
- 2. Spontaneous hematoma $> 25 \text{ cm}^2$
- 3. Excessive wound hematoma (not injection site related)
- 4. Macroscopic hematuria (spontaneous or lasting > 24 hours if associated with an intervention)
- 5. Spontaneous rectal bleeding; epistaxis, gingival bleeding, hemoptysis, hematemesis
- 6. Bleeding after venipuncture for > 5 minutes

Minor bleeding events are those that do not fulfill the criteria for MB or clinically relevant, non-major bleeding events (defined above), for example excess bruising, petechiae, gingival bleeding on brushing teeth.

8.5.5. Safety Monitoring for Constitutional Symptoms

Patients will be instructed to promptly report any signs or symptoms of fever, constitutional symptoms, rash, arthralgia or joint swelling that may arise during the study and the Investigator should closely evaluate all potential causes, including concomitant illness. Patients who experience persistent or increasing symptoms should be tested for ADA and discussed with the Medical Monitor or designee to determine whether additional monitoring or laboratory tests are required.

